- 14 SEL24/MEN1703 will be given once daily on D1-14 over 21-day treatment cycles. Doses shall be taken on an empty stomach (at least 2 hours after and 1 hour before eating).
- 15 Blood samples for plasma PK analysis will be taken at C1 D1 pre-dose, 0.5, 1, 2, 4, 6, 8, 10-14 and 24 h (C1 D2 pre-dose), C1 D7 at 4 and 8 h post dose, C1 D14 (or last day of dosing in cycle) pre-dose, 0.5, 1, 2, 4, 6, 8, 10-14 and 24 h (C1 D15), 72 h (C1 D17), 120 h (C1 D19), C2 D1 pre-dose (-1 d tolerance), D7 and 14 (or last day of dosing in cycle) at 2-6 h post dose, C3 onwards D1 pre-dose (-1 d tolerance) and D14 (or last day of dosing in each cycle) at 2-6 h post dose (-2 d tolerance). All sample times are approximate, and every effort should be made to take the samples as close to the specified time given and, where relevant, contemporaneously with blood sampling for PD biomarker assessments. For the C1 D1, D2, D7 and D14 a  $\pm$  5 min window is allowed, for the C1 last day of dosing 24 h (C1D15), 72 h (C1D17) and 120 h (C1D19) samples, a  $\pm$  2 h window is allowed. Please refer to the Lab Manual for full details on sample collection, time-points, processing, storage and shipment.
- 16 Part 1 only. Urine collection for PK analysis will be collected from the first dose of SEL24/MEN1703 until immediately prior to the second dose. Please refer to the Lab Manual for full details on sample collection, time-points, processing, storage and shipment.
- 17 Final study assessments to be conducted up to 30 d (+/- 2 d) from last dose of SEL24/MEN1703. Adverse events and concomitant medications must be assessed to 30 d from last dose of SEL24/MEN1703. Other assessments may be carried out between 7-30 d from last dose.
- 18 An assessment of each patient's disease status and AML-related medications administered will be made approximately every 3 months from last dose of SEL24/MEN1703 for up to 1 year (or until End of Study, whichever occurs first) regardless of the initiation of additional treatments to determine date of progression (where appropriate) and survival status.

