### **8.3. Completion of the Study**

The study will be completed when all patients have completed their Final Study Visit assessment. On completion of the study, data will be reconciled and the database will be locked for analysis.

Study start is defined by First Patient In (FPI) i.e. when the first patient receives the first dose of study drug. Study Completion is defined by Last Patient Out (LPO) of the study i.e. when the last patient enrolled in the study has completed the last dose of study drug or discontinued for any reason and been followed up to the Final Study Visit.

End of Study is defined as the Final Study Visit of the last subject who discontinues the study treatment.

An addendum (or addenda) to the Clinical Study Report will be generated as required to report any data obtained during the Follow-up Assessments.

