15. Blood samples for plasma PK analysis will be taken at C1 D1 pre-dose, 0.5, 1, 2, 4, 6, 8, 10-14 and 24 h (C1 D2 pre-dose), C1 D7 at 4 and 8 h post dose, C1 D14 (or last day of dosing in cycle) pre-dose, 0.5, 1, 2, 4, 6, 8, 10-14 and 24 h (C1 D15), 72 h (C1 D17), 120 h (C1 D19), C2 D1 pre-dose (-1 d tolerance), D7 and 14 (or last day of dosing in cycle) at 2-6 h post dose, C3 onwards D1 pre-dose (-1 d tolerance) and D14 (or last day of dosing in each cycle) at 2-6 h post dose (-2 d tolerance). All sample times are approximate, and every effort should be made to take the samples as close to the specified time given and, where relevant, contemporaneously with blood sampling for PD biomarker assessments. For the C1 D1, D2, D7 and D14 a ±5 min window is allowed, for the C1 last day of dosing 24 h (C1D15), 72 h (C1D17) and 120 h (C1D19) samples, a ±2 h window is allowed. Please refer to the Lab Manual for full details on sample collection, time-points, processing, storage and shipment.
16. Part 1 only. Urine collection for PK analysis will be collected from the first dose of SEL24/MEN1703 until immediately prior to the second dose. Please refer to the Lab Manual for full details on sample collection, time-points, processing, storage and shipment.
17. Final study assessments to be conducted up to 30 d (+/- 2 d) from last dose of SEL24/MEN1703. Adverse events and concomitant medications must be assessed to 30 d from last dose of SEL24/MEN1703. Other assessments may be carried out between 7-30 d from last dose.
18. An assessment of each patient's disease status will be made approximately every 3 months from last dose of SEL24/MEN1703 for up to 1 year regardless of initiation of additional treatments to determine date of progression (where appropriate) and survival status.

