5.4.2. Secondary endpoints

Study Part 1:

- The number and frequency of AEs, safety laboratory, vital signs and ECG assessments

Study Part 1 and 2:

- Disease assessment will involve evaluation of leukemic blast proportion in the bone marrow. Hematologic parameters from the routine local assessments including blast percentage (where applicable), platelet count, and other relevant parameters such as transfusion dependence will also contribute to this assessment. Disease assessment will also include an aliquot of bone marrow aspirate/biopsy that will be centrally stored for future analysis (e.g. minimal residual disease), if any.
- Overall response rate (ORR), defined as the proportion of patients who have a complete remission (CR), complete remission with incomplete hematologic recovery (CRI), complete remission with partial hematologic recovery (CRh) or morphologic leukemia-free state (MLFS) response to therapy.
- Partial remission (PR) rate, defined as the proportion of patients who have a partial remission response to therapy.
- Duration of response (DoR), defined as the time from the date of first CR, CRI, CRh, CRMRD-, MLFS or PR until the date of documented relapse of any type, progressive disease or death due to disease progression for subjects who achieve CR, CRI, CRh, CRMRD-, MLFS or PR. Subjects who either do not relapse or die without report of relapse are considered nonevents and censored at their last relapse-free disease assessment date. Subjects who undergo an allogeneic HSCT will be considered non events and censored at the time of HSCT

- Relapse free survival (RFS), defined as the time from the date of first CR, CRi, CRh or CRM RD- until the date of documented relapse or death from any cause. Subjects who either do not relapse or do not die are censored at their last relapse-free disease assessment date.
- Event free survival (EFS), defined as the time from the date of first study drug intake until the date of documented relapse, treatment failure or death from any cause. For a subject who did not experience the event, EFS is censored at the date of last relapse-free disease assessment. Subject is not censored at HSCT.
- Overall survival (OS), defined as the number of days between the first study drug administration and death from any cause. Patients without the event are censored at the last date of follow-up.

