11.3. Data imputation

The missing values will not be imputed because, for all the analyses, an observed-cases approach will be applied.

Regarding time-to-event variables analysis:

- OS, if a subject is censored with respect to the event of interest the censoring date is defined as the date of the last performed visit;
- RFS, EFS and DoR, if a subject is censored with respect to the event of interest the censoring date is defined as the date of the last relapse/progression/event-free disease assessment.

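### Duration of response has no stop at a subsequent anti-leukemic drug, although disease status is followed through later treatment; only transplant is covered, and only in SAP 5.4.2

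*SAP*

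**What the plan says.** **Follow-up.** SAP 5.3, footnote 18, has disease status assessed about every 3 months from the last dose, "for up to 1 year regardless of initiation of additional treatments to determine date of progression (where appropriate) and survival status". Protocol Table 5, footnote 18, differs in two ways. It also collects later treatment: "An assessment of each patient's disease status and AML-related medications administered will be made approximately every 3 months". And it stops at End of Study if that comes before 1 year; under Protocol 8.3, "End of Study is defined as the Final Study Visit of the last subject who discontinues the study treatment".

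**Duration of response.** SAP 5.4.2 runs DoR from first response to relapse, progression or death from progression. It has one rule for later treatment: "Subjects who undergo an allogeneic HSCT will be considered non events and censored at the time of HSCT". It does not mention later drugs.

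**RFS and EFS.** For RFS, SAP 5.4.2 says: "Subjects who either do not relapse or do not die are censored at their last relapse-free disease assessment date". EFS is expressly not censored at HSCT. Neither has a rule for a later drug.

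**General rule and formulas.** For RFS, EFS and DoR, SAP 11.3 says that for a censored subject "the censoring date is defined as the date of the last relapse/progression/event-free disease assessment". The 12.1 formulas follow this. Neither section mentions a later drug, and neither repeats the HSCT rule for DoR.

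**Best overall response.** SAP 12.1 counts patients by best response category and gives no assessment window or cut-off.

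**Outputs.** SAP 13.2 covers prior and concomitant medication. It plans no table or listing of therapy given after study drug.

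**The concern.** In a single-arm study DoR is read as how long the study drug holds a response. By censoring at HSCT, the SAP accepts that a later treatment can prolong remission and that this time should not count. It applies the idea to transplant and leaves out drugs.

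Protocol 3.4 and 4.4 allow a responder to stop study drug without relapse, for example for toxicity, need for a prohibited medication or investigator decision. If another agent then maintains the remission, the time counts as DoR for SEL24/MEN1703. With few responders one such patient can set the tail of the curve and move the median, and there is no control arm to reveal it. Without an output on later therapy, a reader of the report could not see which responders were affected.

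There is also a risk inside the SAP: a programmer working from 11.3 and 12.1 alone would not apply even the HSCT rule.

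**Working it through.** The plan gives no figure to reproduce. SAP section 8 states that no formal sample size calculation applies, and neither document gives a response rate, a DoR or a share of responders who switch drug. The check is therefore a comparison of rules, followed by illustrations on stated assumptions.

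**1. What stops each endpoint**

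| Endpoint | At allogeneic HSCT | At a subsequent drug |
|---|---|---|
| DoR | Censored in SAP 5.4.2; omitted in 11.3 and 12.1 | No rule |
| RFS | No rule | No rule |
| EFS | Expressly not censored (5.4.2) | No rule |
| Best overall response | No cut-off | No cut-off |

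**2. Three hypothetical responders (Kaplan-Meier)**

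Two relapse at 3 and 4 months. The third stops study drug in remission, starts another drug just after an assessment at 2 months, and relapses at 10.

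- As the SAP is written, events fall at 3, 4 and 10. S(3) = 2/3 = 0.67 and S(4) = 0.67 × 1/2 = 0.33, so the median is 4 months and the tail runs to 10.
- With the third censored at 2 months, two are at risk at 3. S(3) = 1/2 = 0.50 and S(4) = 0. The curve lies at exactly 0.50 from 3 to 4 months. The median is 3 if the first time at or below 0.50 is taken, and (3 + 4)/2 = 3.5 by the midpoint convention. The tail ends at 4.

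The median shifts by 0.5 to 1 month and the tail by 10 − 4 = 6 months.

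**3. Simulation of 400,000 responders**

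Assumptions, none from the documents: true median DoR 3.0 months with exponential times; switches 0.5 to 3 months after response, unrelated to relapse risk; median time to relapse after a switch 6 or 12 months.

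| Share switching before relapse | Median DoR, no stop at new drug | Median DoR, censored at switch |
|---|---|---|
| 0% | 3.0 | 3.0 |
| 17% | 3.2 to 3.3 | 3.0 |
| 34% | 3.5 to 3.9 | 3.0 |

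Each range runs from the 6-month to the 12-month assumption.

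**4. Response rate**

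One wrongly credited response adds 1/20 = 5.0 percentage points in a cohort of 20, or 1/23 = 4.3 in the 23 all-comers. For example, 2/20 = 10.0% (exact 95% CI 1.2 to 31.7) becomes 3/20 = 15.0% (3.2 to 37.9).

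The routes are limited. SAP footnote 8 ties disease evaluation to a marrow sample, the flow chart marks neither in the Follow Up column, and Protocol 5.1 allows the contact to be a telephone call. What remains is a Final Study Visit marrow taken after new therapy has begun (the visit may be up to 30 days after the last dose), an unscheduled marrow, or a marrow after HSCT, which SAP 5.1 foresees.

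**The case against.** **Following patients regardless of later therapy is a legitimate choice.** Both documents state it, and it is a sound basis for OS and defensible for EFS and RFS. This stands, and those analyses should remain. It does not settle DoR, where the SAP already departs from that approach at HSCT.

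**The situation may be rare.** Patients who stop for progression already have their DoR event, anti-cancer drugs barred by the exclusion criteria are not allowed on study, and entry requires that no standard option is available. The documents give no frequency, so this stands as a limit on size. The footnotes nevertheless anticipate further treatment.

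**Follow-up is limited.** It lasts at most a year and can end sooner at End of Study, and Protocol 8.3 puts follow-up data in a report addendum as required. This shortens follow-up for patients who stop late. One who stops early can still complete the year before the last subject's Final Study Visit. The SAP does not say whether a telephone contact counts as a disease assessment for censoring, but a relapse first reported there is an event on either reading.

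**Censoring at a switch can itself mislead.** If the switch reflects toxicity or early loss of response, the censoring is informative. In the three-patient example it removes one of three events. This stands, and is why both versions are needed.

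**Stronger readings.** A reader might infer that no endpoint stops at any next treatment; the HSCT rule for DoR in SAP 5.4.2 contradicts that. A reader might also infer that the follow-up year feeds responses into ORR. Its stated purpose is progression date and survival, and it has no scheduled marrow, so the documents do not support that.

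**Conclusion.** The SAP has no rule for a subsequent anti-leukemic drug in DoR, and its one rule for later treatment appears in 5.4.2 but not in 11.3 or 12.1. As written, remission time under another drug counts toward DoR for SEL24/MEN1703.

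The size cannot be known from the documents. On the assumptions above, the median DoR is overstated by about 0.2 to 0.9 months with 17% to 34% of responders switching. One patient among three can move it by 0.5 to 1 month and extend the tail by 6. The missing cut-off for best response is a lesser gap, worth about 4 to 5 percentage points per affected patient and confined to the marrows listed above.

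All these endpoints are secondary and descriptive. The Part 2 primary endpoint is safety and is unaffected, so the point does not put the study's main conclusion in doubt. It should be corrected because anti-leukemic activity is a stated secondary objective and the correction is cheap.

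**What to change.** In SAP 11.3 and 12.1:

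- **(a) Response.** Take best overall response, ORR and PR rate only from assessments before the first subsequent anti-leukemic therapy or HSCT.
- **(b) DoR.** Censor at the last disease assessment before the first subsequent anti-leukemic therapy. Repeat the 5.4.2 rule, which censors at the time of HSCT itself; the two censoring dates differ and should be stated separately. Report DoR without the new-therapy censoring as a sensitivity analysis.
- **(c) RFS and EFS.** Keep both regardless of subsequent therapy and say so. Add RFS censored at the start of that therapy as a sensitivity analysis.

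Use the AML-related medications collected under Protocol Table 5, footnote 18, and list them by patient with start dates. Restoring the item to SAP footnote 18 is clerical, since the protocol already governs its collection.

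**Cost.** SAP text, one derived date, one listing and two sensitivity analyses. No new procedure is needed, provided that start dates are recorded with these medications; the protocol does not say so explicitly. The statistical price is more censoring in DoR, possibly informative, which is why both versions are shown.

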5.4. Study Endpoints

5.4.1. Primary endpoints

Study Part 1:

- DLT evaluation at the end of one treatment cycle for each dose level.

Study Part 2:

- The number and frequency of AE, safety laboratory, vital signs and ECG assessments.

5.4.2. Secondary endpoints

Study Part 1:

- The number and frequency of AEs, safety laboratory, vital signs and ECG assessments

Study Part 1 and 2:

- Disease assessment will involve evaluation of leukemic blast proportion in the bone marrow. Hematologic parameters from the routine local assessments including blast percentage (where applicable), platelet count, and other relevant parameters such as transfusion dependence will also contribute to this assessment. Disease assessment will also include an aliquot of bone marrow aspirate/biopsy that will be centrally stored for future analysis (e.g. minimal residual disease), if any.
- Overall response rate (ORR), defined as the proportion of patients who have a complete remission (CR), complete remission with incomplete hematologic recovery (CRI), complete remission with partial hematologic recovery (CRh) or morphologic leukemia-free state (MLFS) response to therapy.
- Partial remission (PR) rate, defined as the proportion of patients who have a partial remission response to therapy.
- Duration of response (DoR), defined as the time from the date of first CR, CRI, CRh, CRMRD-, MLFS or PR until the date of documented relapse of any type, progressive disease or death due to disease progression for subjects who achieve CR, CRI, CRh, CRMRD-, MLFS or PR. Subjects who either do not relapse or die without report of relapse are considered nonevents and censored at their last relapse-free disease assessment date. Subjects who undergo an allogeneic HSCT will be considered non events and censored at the time of HSCT

- Relapse free survival (RFS), defined as the time from the date of first CR, CRi, CRh or CRM RD- until the date of documented relapse or death from any cause. Subjects who either do not relapse or do not die are censored at their last relapse-free disease assessment date.
- Event free survival (EFS), defined as the time from the date of first study drug intake until the date of documented relapse, treatment failure or death from any cause. For a subject who did not experience the event, EFS is censored at the date of last relapse-free disease assessment. Subject is not censored at HSCT.
- Overall survival (OS), defined as the number of days between the first study drug administration and death from any cause. Patients without the event are censored at the last date of follow-up.
- Evaluation of CYP2D6 phenotyping will be carried out. As SEL24/MEN1703 may both inhibit and act as a substrate for Cytochrome P450 enzyme CYP2D6, patients will be assessed for their CYP2D6 phenotype. A blood sample collected during Screening will be used for this assessment and results will be reported separately.

Study Part 2:

- Transfusion conversion rate, defined as the number of subjects who were transfusion dependent at baseline period but become transfusion independent at post-baseline period divided by the total number of subjects who were transfusion dependent at baseline period.
- Transfusion maintenance rate, defined as the number of subjects who were transfusion independent at baseline period and still maintain transfusion independent at post-baseline period divided by the total number of subjects who were transfusion independent at baseline period.
- Allogeneic HSCT rate, defined as the percentage of subjects undergoing allo-HSCT during the study period.

Both transfusion conversion rate and maintenance rate apply to subjects who have evaluable post-baseline transfusion status.

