Hematologic relapse (after CR MRD -, CR, CR i , CRh)	Bone marrow blasts $\geq 5\%$ ; or reappearance of blasts in the blood; or development of extramedullary disease	
Molecular relapse (after CR MRD -)	If studied pretreatment, reoccurrence of MRD as assessed by RT-qPCR or by MFC	Test applied, sensitivity of the assay, and cutoff values used must be reported; analyses should be done in experienced laboratories (centralized diagnostics)

Table adapted from Döhner H, *et al* 2017

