7. Bone marrow aspirate/biopsy shall be taken at the following time points: at Screening, either as soon as peripheral lab results become consistent with an objective response or at C3 D1 whichever comes first, at a recommended frequency of every 2 cycles thereafter e.g. C5 D1, C7 D1, etc. (-2 d tolerance) or as clinically indicated, at relapse and FSV. In case of AML relapse following response to SEL24/MEN1703, a bone marrow aspirate/biopsy is highly recommended, whenever possible. Time-points described as (X)§ are recommended every 2 cycles, but not mandatory. Patients may not have the FSV assessment performed where they already have had a bone marrow assessment in the last month or have progressive disease. A bone marrow differential will be performed locally. An aliquot of bone marrow aspirate/biopsy will be centrally stored for future analysis (e.g. minimal residual disease), if any. Please refer to the Lab Manual for full details on bone marrow aspirates/biopsy collection, time-points, processing, storage and shipment.
8. Disease evaluation will be performed at every time-point (excluding Screening) where a bone marrow aspirate/biopsy is taken.
9. Bone marrow aspirate/biopsy taken during the study will be tested centrally for the genetic profile of AML cells. Please refer to the Lab Manual for full details on sample collection, time-points, processing, storage and shipment.
10. Blood sampling for PD biomarker assessments will be taken at Screening, C1 D1 pre-dose, C1 D1 2-6h post-dose, C1 D14 2-6h post-dose, C2 D1 pre-dose, C2 D14 2-6h post-dose, C3 D1 pre-dose, C3 D14 2-6h post-dose. All sample times are approximate and every effort should be made to take the samples as close to the specified time given and, where relevant, contemporaneously with blood sampling for PK assessments. For the C1 D1 and D14 a ±30 min window is allowed. Please refer to the Lab Manual for full details on PD biomarker sample collection, time-points, processing, storage and shipment.
11. CYP2D6 phenotyping will be assessed centrally on a blood sample collected at Screening.
12. CD25 expression will be assessed centrally on an aliquot of blood sample for PD biomarker assessment taken at Screening.
13. Mutational status (including at least FLT3 and IDH mutations) will be assessed locally at Screening.
14. SEL24/MEN1703 will be given once daily on D1-14 over 21-day treatment cycles. Doses shall be taken on an empty stomach (at least 2 hours after and 1 hour before eating).

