12.1. Efficacy analysis

The Overall Survival (OS) is calculated as:

- In case of all-cause death:
 $OS = date\ of\ death - date\ of\ first\ study\ drug\ administration + 1;$
- In case of censored information not for drop-out:
 $OS = date\ of\ end\ of\ observation\ period\ (i.e.\ study\ end / end\ of\ survival\ follow-up) - date\ of\ first\ study\ drug\ administration + 1;$
- In case of censored information for drop-out:
 $OS = last\ date\ known\ alive - date\ of\ first\ study\ drug\ administration + 1.$

The Relapse Free Survival (RFS) is calculated as:

- In case of relapse or all-cause death:
 $RFS = date\ of\ relapse\ or\ death\ (whichever\ comes\ first) - date\ of\ first\ CR,\ CRi,\ CRh\ or\ CR_{MRD-} + 1;$
- In case of censored information:
 $RFS = date\ of\ last\ relapse-free\ disease\ assessment - date\ of\ first\ CR,\ CRi,\ CRh\ or\ CR_{MRD-} + 1.$

The Event Free Survival (EFS) is calculated as:

- In case of relapse, treatment failure or all-cause death:
 $EFS = date\ of\ relapse,\ disease\ progression,\ treatment\ failure\ (failure\ to\ achieve\ CR/CRh/CRi/CR_{MRD-}\ after\ at\ least\ five\ cycles\ of\ treatment)\ or\ death\ (whichever\ comes\ first) - date\ of\ first\ study\ drug\ administration + 1;$
- In case of censored information:
 $EFS = date\ of\ last\ relapse-free/treatment-failure-free/progression-free\ disease\ assessment - date\ of\ first\ study\ drug\ administration + 1.$

The Duration of Response (DoR) is calculated as:

- In case of relapse, progressive disease or death due to progressive disease:
 $DoR = date\ of\ relapse\ of\ any\ type/progressive\ disease/death\ due\ to\ progressive\ disease - date\ of\ first\ CR,\ CRi,\ CRh,\ CR_{MRD-},\ MLFS\ or\ PR + 1;$
- In case of censored information:
 $DoR = date\ of\ last\ relapse-free\ disease\ assessment - date\ of\ first\ CR,\ CRi,\ CRh,\ CR_{MRD-},\ MLFS\ or\ PR + 1.$

No formal statistical analysis will be performed on anti-leukemic parameters.

Anti-leukemic activity data will be collected throughout Part 1 and Part 2 and will be summarized by cohort, by dose and overall.

Measures of anti-leukemic activity will be computed on both safety and efficacy populations and they will include:

- Changes (absolute and %) in pre- and post-treatment levels of leukemic blasts in the peripheral blood and/or bone marrow;
- Number and percentages of patients who reported as best overall response one of the following: CRM RD-, CR, CRh, CRi, MLFS, PR, SD, PD;
- Duration of response (DoR);

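### SAP 5.4.2 and 12.1 conflict on whether a progression death without reported relapse is a DoR event, and both censor responders' relapse-free deaths from other causes

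*SAP*

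**What the plan says.** - **SAP 5.4.2, event.** DoR runs from the first CR, CRi, CRh, CRMRD-, MLFS or PR "until the date of documented relapse of any type, progressive disease or death due to disease progression".
- **SAP 5.4.2, censoring (the next sentence).** "Subjects who either do not relapse or die without report of relapse are considered nonevents and censored at their last relapse-free disease assessment date". No exception is made for a death from progression.
- **SAP 12.1, calculation.** The event branch for DoR reads "In case of relapse, progressive disease or death due to progressive disease". Everything else falls into the censored branch, dated at the last assessment free of relapse.
- **SAP 11.3, censoring date.** For RFS, EFS and DoR, "the censoring date is defined as the date of the last relapse/progression/event-free disease assessment".
- **SAP 11.2.** Time-to-event variables are summarised by Kaplan-Meier curves and by the median with its 95% CI.
- **Other endpoints in SAP 5.4.2.** RFS runs "until the date of documented relapse or death from any cause", but only for CR, CRi, CRh or CRMRD- responders. EFS and OS also count death from any cause, starting at first dose.
- **Protocol.** Table 2 and Section 8.9 list DoR without defining its events or censoring, so the protocol cannot settle the matter. Appendix D defines hematologic relapse only after CRMRD-, CR, CRi or CRh, not after MLFS or PR.

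**The concern.** There are two separate problems.

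First, the text does not give one rule. Two programmers, one working from the censoring sentence in 5.4.2 and one from the formula in 12.1, would code the same progression death differently. The case is realistic. After Cycle 3, marrow sampling is only "at a recommended frequency of every 2 cycles thereafter", the final-visit marrow may be skipped in progressive disease (SAP 5.3, footnote 7), and off-treatment follow-up is every 3 months and may be by telephone (Protocol 5.1). A responder can therefore die of leukemia with no relapse on record.

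Second, whichever text governs, a responder who dies relapse-free of another cause is censored at an assessment before death. Kaplan-Meier then treats that patient as someone who could still relapse later. Compared with a DoR that counts death from any cause, the curve sits too high. DoR is the only one of the four time-to-event endpoints that does this, and a reader of the report may take it for an all-cause measure.

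**Working it through.** **1. The rules side by side**

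| Course of a responder | 5.4.2, event sentence | 5.4.2, censoring sentence | 12.1 |
|---|---|---|---|
| Relapse documented, then death | Event at relapse | Does not apply | Event at relapse |
| Death from progression, no relapse reported | Event | Censored | Event |
| Death from another cause, no relapse | Not listed | Censored | Censored |
| MLFS or PR responder with documented PD | Event at PD | Literally no relapse, so censored | Event at PD |

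Rows 2 and 4 are contradictions within 5.4.2. Row 3 is consistent across sections and is the censoring issue.

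**2. Inputs for the size**

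The SAP states no DoR median, event count or sample size based on DoR, so there is no figure to reproduce.

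- From the documents: marrow assessment about every 2 cycles, 2 x 21 = 42 days, about 1.4 months; 3-monthly follow-up off treatment.
- Assumed: exponential times; all-cause median 4.0 months; a share q of 10-40% of first events being relapse-free deaths; half of those deaths due to progression.

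**3. Formulas and results**

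The total hazard is h = ln 2 / 4.0 = 0.173 per month, split into relapse h(1 - q) and relapse-free death hq. If deaths were censored on the day of death, the Kaplan-Meier median would be

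- literal 5.4.2 sentence: 4.0/(1 - q);
- 12.1 with half the deaths due to progression: 4.0/(1 - q/2).

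The SAP censors earlier, at the last assessment. That shrinks the risk set sooner and lowers these values somewhat. Simulation with 20,000 responders per setting and a 1.4-month gap gave (months):

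| q | All-cause | 5.4.2, closed form | 5.4.2, simulated | 12.1, closed form | 12.1, simulated |
|---|---|---|---|---|---|
| 10% | 4.00 | 4.44 | 4.38 | 4.21 | 4.18 |
| 20% | 3.99 | 5.00 | 4.86 | 4.44 | 4.37 |
| 30% | 3.91 | 5.71 | 5.43 | 4.71 | 4.53 |
| 40% | 3.93 | 6.67 | 6.15 | 5.00 | 4.77 |

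Against 4.0 months, the literal sentence adds about 10% (4.38/4.0) to 54% (6.15/4.0), and 12.1 adds about 5% (4.18/4.0) to 19% (4.77/4.0). With a 3-month gap the simulated ranges are 4.33-6.06 and 4.16-4.69.

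**4. A case that can be checked by hand**

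Six responders: relapses at 2, 4, 6 and 8 months; relapse-free deaths at 3 and 5 months, last assessed at 2.5 and 4.5. The median is the first time the curve is at or below 0.5.

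- Literal 5.4.2: 5/6 = 0.833 at month 2; x 3/4 = 0.625 at month 4; x 1/2 = 0.313 at month 6. Median 6.
- All deaths as events: 3 of 6 remain after month 4. Median 4.
- 12.1, with the month-3 death due to progression: 5/6 x 4/5 x 3/4 = 0.5 at month 4. Median 4, equal to the all-cause median here.

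**5. Small samples**

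With 5 or 10 responders, q of 20% or 40% and either gap, the literal rule gave a longer median than the all-cause rule in 20-92% of simulated sets, the same in 8-74% and a shorter one in 0-7%. A reversal needs a long gap before death: relapses at 5 and 20 months and a death at 10 months last assessed at month 1 give a median of 5 with censoring and 10 with death as an event.

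**6. Cumulative incidence on the same model**

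Relapse incidence is (1 - q)(1 - exp(-ht)). It reaches 50% at -ln(0.375)/0.173 = 5.7 months for q = 20% and at -ln(0.25)/0.173 = 8.0 months for q = 1/3. Censoring at death gives Kaplan-Meier medians of 5.0 and 6.0 for the same q.

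**The case against.** **SAP 12.1 is the operative formula.** From 5.4.2 alone, a reader might infer that the plan discards every death without reported relapse. The documents do not support that as the settled rule, because both the event sentence in 5.4.2 and the formula in 12.1 keep progression deaths as events. This stands. If 12.1 governs, only other-cause deaths are censored and the smaller range applies.

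**A relapse-or-progression DoR is a legitimate choice.** This also stands, and it limits what may be called bias. The curve reads long only against an all-cause target. Against cumulative incidence of relapse it reads short (step 6). But the SAP does not say it intends a cause-specific measure, it gives no procedure for attributing cause of death, and its other three time-to-event endpoints count all deaths.

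**The deaths are visible elsewhere.** RFS covers CR-type responders, EFS and OS cover all treated patients, and SAP 13.2.1 tabulates adverse events leading to death (Tables 2.5.2 and 2.5.3). A reader might infer that toxicity deaths are hidden; they are not. What remains is that no endpoint measured from response counts other-cause deaths in MLFS and PR responders.

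**Larger figures are easy to produce.** A reader might apply 4.0/(1 - q) at 20%, 33% and 50% and report 5.0, 6.0 and 8.0 months. Those values censor at death and use the harsher sentence. With the SAP's dating the literal rule gives about 4.9, 5.8 and 7.5. Under 12.1 with half the deaths due to progression, it gives about 4.4, 4.7 and 5.2. A doubling is not supported.

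**The safety link is conditional.** Protocol 1.5 speaks of a potential risk of fatal thrombosis and severe hepatotoxicity. The one fatal treatment-related DLT described was at 150 mg, whereas Part 2 uses 125 mg. No document reports a relapse-free death in a responder, so such deaths could lengthen DoR, not that they will.

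**Conclusion.** The conflict is in the current text: SAP 5.4.2 contradicts itself and 12.1 on progression deaths without reported relapse, and its wording does not fit MLFS and PR responders with PD. Separately, relapse-free responder deaths from other causes are censored at the last assessment under every reading, which in general gives a longer DoR than one counting death from any cause.

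The size cannot be derived from the documents. Under the stated assumptions, a 4.0-month all-cause median reads as about 4.4-6.2 months under the literal 5.4.2 sentence and about 4.2-4.8 under 12.1. With no relapse-free responder deaths there is no effect, and in very small samples the median may be unchanged or occasionally shorter.

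DoR is secondary and descriptive, with no test or sample size resting on it, so the consequence is for interpretation only. It should still be corrected, because the reported curve depends on which section the programmer follows.

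**What to change.** 1. Use one rule in SAP 5.4.2, 11.3 and 12.1: DoR ends at the earliest of documented relapse, PD or death from any cause, with deaths dated at death.
2. Censor only responders alive with neither relapse nor PD, at the last assessment showing neither. Naming PD beside relapse covers MLFS and PR responders.
3. Keep the present rule, as in 12.1, as a labelled sensitivity analysis, and state who assigns cause of death for it.
4. If a relapse/PD-only view is also wanted, report cumulative incidence with death as a competing event. Say that it answers a different question and will not shorten the estimate.
5. In the same edit, settle transplant. Section 5.4.2 says "Subjects who undergo an allogeneic HSCT will be considered non events and censored at the time of HSCT", but 11.3 and 12.1 do not carry this.

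Cost: SAP wording and one censoring flag. Survival status is already collected at follow-up (SAP 5.3, footnote 18), so no new data are needed. The downside is that the reported DoR may be shorter, by an amount that depends on how many responders die relapse-free.
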